#### **4.3. Product registration and the reason for clinical trial registration in China**

INTERCEED™ first passed the BSI Design Examination in November 2002 and obtained the EC Design-Examination Certificate. The “Design-Examination Certificate” was extended in February 2015.

This product has been applied in clinical practice in many countries around the world, including many EU, USA, Canada, Latin American countries, Asia-Pacific countries, Middle Eastern and African countries.

This product has not been used in general abdominal operations in Chinese population. Therefore, the clinical study is designed to support the registration of the product in China.

### **5. Features, structural composition, operation principle, mechanism of action and study population**

#### **5.1. Features**

##### **5.1.1. Design Features of Study Product**

INTERCEED™ is a sterile, single-use-only, absorbable off-white knitted fabric prepared by the controlled oxidation of regenerated cellulose. INTERCEED™ is applied dry in general abdominal and gynecological operations, after meticulous hemostasis has been achieved, in order to reduce the occurrence of postoperative adhesions.

[figure not shown]
INTERCEED™ reduces the formation of adhesions by physically separating the surfaces of tissues that are adjacent to each other during the reperitonealization phase.

When used as directed, INTERCEED™ is easy to apply and is absorbed from the site of implantation within four weeks. Absorption rate depends upon several factors, including the amount used and implantation site.

#### 5.1.2. Material Features of Study Product

INTERCEED™ is a sterile, single-use-only, absorbable off-white knitted fabric prepared by the controlled oxidation of regenerated cellulose. The oxidized regenerated cellulose knitted fabric is woven of 60D and 24-strand lustrous rayon. See **Fig. 1** below.

**Fig. 1** Picture of INTERCEED™

[figure not shown]

INTERCEED™

Enlarged view of knitted fabric

The oxidized regenerated cellulose is a copolymer composed of 68-80 mole percentage of uronic acid and 20-32 mole percentage of glucosyl group. The carboxyl group content is 12%-18%.

The chemical structural formula is as follows.

#### 5.2. Structural Composition, Operation Principle and Mechanism of Action

- 5.2.1. The study product is a sterile, single-use-only, absorbable off-white knitted fabric prepared by the controlled oxidation of regenerated cellulose.
- 5.2.2. The operation principle and mechanism of action of the study product are to reduce the formation of adhesions by physically separating the surfaces of tissues that are adjacent to each other during the reperitonealization phase.

#### 5.3. Study Population

The study population will include 220 subjects scheduled to undergo laparoscopic radical resection of rectal carcinoma with preventive loop ileostomy.

## **6. INDICATIONS AND CONTRAINDICATIONS, PRECAUTIONS**

### **6.1. Indications:**

INTERCEED™ is indicated as an adjuvant in general abdominal and gynecological pelvic surgery for reducing the incidence, extent and severity of postoperative abdominal adhesions after meticulous hemostasis has first been achieved.

### **6.2. Contraindications:**

INTERCEED™ is contraindicated in the presence of frank infection.

INTERCEED™ is not indicated as a hemostatic agent. Appropriate means of achieving hemostasis must be employed.

### **6.3. Precautions:**

Use only a single layer of INTERCEED™, since multiple layers of packing or folding will not enhance the adhesion barrier characteristics and may interfere with the absorption rate of INTERCEED™. Care should be exercised in applying INTERCEED™ to a pelvic or abdominal organ not to constrict or restrict it.

Wrapping directly around gastrointestinal anastomoses is not recommended.

If the product comes in contact with blood prior to completing the procedure, it should be discarded, as fibrin deposition cannot be removed by irrigation and may promote adhesion formation.

The safety and effectiveness of using INTERCEED™ in combination with other adhesion-prevention treatments have not been clinically established.

INTERCEED™ is supplied sterile. As the material is not compatible with autoclaving or ethylene oxide sterilization, INTERCEED™ must not be resterilized.

Foreign-body reactions may occur in some patients.

Interactions may occur between INTERCEED™ and some drugs used at the surgical site.

Pathologists examining sites of INTERCEED™ placement should be made aware of its usage and of the normal cellular response to INTERCEED™ to facilitate proper evaluation of specimens.

There is no evidence to suggest, or reason to believe, that the use of INTERCEED™ has any deleterious effect on the mother or fetus when used during pregnancy or that the product or its breakdown products would have an effect on lactation. However, ectopic pregnancies have been associated with fertility surgery of the female reproductive tract. No adequate and well-controlled studies have been conducted in women who become pregnant within the first month after exposure to INTERCEED™. No data exist to establish the effect, if any, of INTERCEED™ on the occurrence of ectopic pregnancies. No teratogenic studies have been performed. Therefore, an avoidance of conception should be considered during the first complete menstrual cycle after use of INTERCEED™.

## 7. OVERALL DESIGN

### 7.1. Trial Design

#### 7.1.1. Trial Objective

The primary objective of this study is to evaluate the efficacy and safety of INTERCEED™ in reducing the incidence of adhesions at the target incision site in patients undergoing laparoscopic colorectal surgery.

#### 7.1.2. Trial Endpoint

##### Primary Endpoints

The primary endpoint is defined as the proportion of subjects with adhesions at the target incision site in each study group.

The assessment of adhesions will be conducted during the second laparoscopy for ileostomy reversal.

The primary endpoint will be assessed by means of reviewing the imaging data by independent central reviewers who will be blinded to the study treatment groups. The image data is defined as the video which is not shorter than 30 seconds taken through laparoscopy during Phase 2 operation and allowing an observation of the entire product application site and surrounding areas in the treatment group or the target incision site in the control group.

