#### **3.2. Contents of Clinical Trial**

The study population will enroll 220 subjects scheduled to undergo laparoscopic colorectal carcinoma radical resection with preventive ileostomy. The enrolled subjects will be randomly divided in two groups in a 1:1 ratio: the study group and control group, of which the INTERCEED™ is applied in the study group, and no adhesion barrier for subjects in the control group.

In this study, a follow-up period of 9 months will be required for the eligible subjects. The primary endpoint is defined as the proportion of subjects free of adhesions at the target incision site in each study group. The target incision site in this study is a midline incision mainly for removal the specimen. The assessment of adhesions will be conducted during the second laparoscopy for ileostomy reversal. The study hypothesis is that the occurrence of postoperative target incision site adhesions in the study group using INTERCEED™ would be lower than that in the control group.

The Phase 1 operation is defined as laparoscopic rectal carcinoma radical resection (R0 resection) with preventive terminal ileostomy; and the Phase 2 operation is defined as ileostomy reversal and laparoscopic exploration between 3 months to 9months after Phase I operation.

Secondary endpoints of the study include: a) extent and severity of adhesions at the target incision site and four abdominal quadrants; b) incidence of mechanical ileus; c) Incidence of surgical site infections; d) Incidence of postoperative all layer wound dehiscence; e)

incidence of delayed wound healing; f) any adverse events and g) study product defects.

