- Any physical or psychological conditions that at discretion of investigators may impair study participation;
- A medical condition or other serious conditions that will interfere with compliance and/or ability to complete this study protocol; or
- Any other situation or reason that at discretion of investigators is unsuitable for study participation.

**3) Any other situation or reason that at discretion of investigators is unsuitable for study participation. Criteria and Procedure of Withdrawal of Subjects from Study**

In accordance with the current revision of the Declaration of Helsinki, a subject has the right to withdraw from the study at any time for any reason without prejudice to their future medical care by the physician or the institution. Should a subject (or subject's legally authorized guardian/representative) decide to withdraw, 1) all data collected up to the point of withdrawal will be considered for analysis; and 2) all efforts will be made to collect and report the final visit

observations as thoroughly and timely as possible. The primary reason for early withdrawal will be recorded on the electronic case report form (eCRF). The criteria for withdrawal of subjects from study including but not limited the following:

**Withdrawal of consent:** Any method of contact with the subject in which they state they no longer want to participate in the study specific activities constitutes withdrawal of consent for participation in the study. This decision must be “self-determination” and should be documented in the electronic case report form (eCRF);

**Physician's determination:** the investigator may determine the withdrawal of subjects from study according to the reasonable medical judgement;

**Adverse event:** the adverse event or serious adverse event may not cause the subjects to discontinue the study treatment. If the investigator decides to withdraw a subject from the study, this subject must be followed up, until the adverse event is resolved or until the stable clinical endpoint is reached;

**Death:** The cause of death will be documented; If the cause of death is related to incisional adhesions which is judged by investigators, the subject will not be withdrawn from the study.

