#### **Termination by the Sponsor, Data Safety Monitoring Board or health authorities;**

Other:

1. Tumor recurrence or intra-abdominal metastasis of primary rectal cancer within the follow-up period;
2. The subject undergoes a second abdominal operation that doesn't meet the definition of Phase 2 operation (see Section 3.2) within the follow-up period and without the image data as described in the Section 7.1.2.. The abdominal operation included but not limited to:
  - a. Operation for an obstructive ileus or other critical anatomical structure (e.g. vessel, nerve) compression;
  - b. Other abdominal operations before the scheduled Phase 2 operation;
  - c. The Phase 2 operation conducted sooner than 3 months or didn't conduct within 9 months after Phase 1 operation;
3. The subject experienced anastomotic leakage (Class B and C) after Phase 1 operation [23];
4. The subject received postoperative radiotherapy after Phase 1 operation;

5. Any intervention that may affect adhesion formation or wound healing at the target incision site judged by the investigator.

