## **8.7. Statistical Method of All Data, together with the Handling Method of Missing, Unused and Error Data (including Termination and Withdrawal Halfway) and Unreasonable Data**

All study endpoints will be analyzed using the available data. There will be no missing data imputation in this study.

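### The plan gives no primary outcome to a subject whose adhesions block the Phase 2 video or prevent laparoscopy, and its missing-data and denominator rules treat that subject in opposite ways

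*Protocol*

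**What the plan says.** **Source of the endpoint.** Protocol 7.1.2: "The primary endpoint will be assessed by means of reviewing the imaging data by independent central reviewers", who are blinded. The image data must be a video that lasts 30 seconds or more and is "taken through laparoscopy during Phase 2 operation and allowing an observation of the entire product application site". For INTERCEED subjects the required field also takes in the neighbouring area; for controls it is only the target incision.

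**Second operation.** Protocol 3.2: "the Phase 2 operation is defined as ileostomy reversal and laparoscopic exploration between 3 months to 9months after Phase I operation". In 7.1.5, item 2 of the other withdrawal reasons covers a second abdominal operation that does not meet this definition, "within the follow-up period and without the image data as described in the Section 7.1.2".

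**Death.** Protocol 7.1.5: "If the cause of death is related to incisional adhesions which is judged by investigators, the subject will not be withdrawn from the study". No primary outcome is assigned to such a subject.

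**Missing data.** Protocol 8.7: "All study endpoints will be analyzed using the available data", and nothing is imputed. SAP 2.3.5 also leaves the primary analysis unimputed but adds a multiple-imputation (MI) sensitivity analysis. Its predictors are age, gender, randomized treatment, baseline radiotherapy or chemotherapy, and Phase 1 variables.

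**Denominator.** Protocol 8.1 and SAP 3.3.1 divide the number free of adhesions by all subjects randomized to the arm. SAP 2.1 uses non-missing subjects unless another rule is specified.

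**Interim.** SAP 4 lists subjects who withdrew before Phase 2 among those included, but the arm sizes in its conditional power (CP) formula count only subjects with an evaluable primary endpoint.

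**The concern.** A verdict of adhesion-free needs a view of the whole site. A verdict of adhesion present needs only one visible adhesion. The plan sets one image standard for both and has no fallback when adhesions are the reason the standard is not met.

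The clearest case is a reversal done without laparoscopy because of adhesions. It falls outside the Phase 2 definition and produces no video, so the subject is withdrawn and has no outcome for the available-data analysis. An adhesion-related death before Phase 2 stays in the study but also has no video. In both cases missingness depends on the outcome. The observed adhesion rate among evaluable subjects then falls below the true rate, and the treatment difference can be distorted in both the final analysis and the interim stopping rule.

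**Working it through.** **1. The plan's own figures.** The sample size (Protocol 8.2.1) uses adhesion rates of 0.50 and 0.75, one-sided alpha 0.025 and power 90%. With pooled variance under the null:

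n = [1.960·√(2·0.625·0.375) + 1.282·√(0.50·0.50 + 0.75·0.25)]² / 0.25² = (1.342 + 0.848)² / 0.0625 ≈ 76.7, so 77 per arm. Then 77/0.70 = 110. Both figures reproduce, so this point does not rest on a sample-size error.

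The SAP Table 4 entries checked (rows −0.02, −0.10, −0.12 and −0.18) also reproduce when the critical-value term carries the final information. With σ² = 0.625·0.375 = 0.2344, I_k = 23.5/0.2344 = 100.27 at 94 subjects and I_K = 38.5/0.2344 = 164.27. For an observed difference of size d:

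CP = Φ[(100.27·d − 1.960·√164.27 + 0.25·64.0)/√64.0] = Φ[(100.27·d − 9.12)/8].

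At d = 0.10 this is 0.55 and at d = 0.18 it is 0.87, as tabulated.

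**2. Effect of outcome-dependent loss.** Let p be the true adhesion rate in an arm and q the share of its adhesion cases made non-evaluable by their adhesions. The observed rate among evaluable subjects is p(1−q)/(1−pq). The documents give no q. Every q below, and the 0.30 v 0.15 rates, are assumptions.

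| True rates, control v INTERCEED | q control / q INTERCEED | Observed rates | Difference | CP at 94 |
|---|---|---|---|---|
| 0.30 v 0.15 | 0 / 0 | 0.300 v 0.150 | 0.150 | 0.77 |
| 0.30 v 0.15 | 5% / 5% | 0.289 v 0.144 | 0.146 | 0.75 |
| 0.30 v 0.15 | 20% / 20% | 0.255 v 0.124 | 0.132 | 0.69 |
| 0.30 v 0.15 | 30% / 10% | 0.231 v 0.137 | 0.094 | 0.51 |
| 0.30 v 0.15 | 10% / 30% | 0.278 v 0.110 | 0.168 | 0.83 |
| 0.75 v 0.50 | 20% / 20% | 0.706 v 0.444 | 0.261 | not computed |
| 0.75 v 0.50 | 20% / 0 | 0.706 v 0.500 | 0.206 | not computed |
| 0.75 v 0.50 | 0 / 20% | 0.750 v 0.444 | 0.306 | not computed |

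Example, third row: 0.30·0.80/(1 − 0.06) = 0.24/0.94 = 0.255 and 0.15·0.80/(1 − 0.03) = 0.12/0.97 = 0.124.

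At the planning rates, with 77 per arm reaching Phase 2, Wald power is 0.913 without loss and 0.890 with 20% lost in both arms. It is 0.729 with 20% lost in control only and 0.976 with 20% lost in INTERCEED only.

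**3. The two denominators.** At the planning rates, suppose 30% are missing regardless of outcome. The available-data proportions free are 0.50 and 0.25, a difference of 0.25. With all randomized subjects in the denominator they are 0.70·0.50 = 0.35 and 0.70·0.25 = 0.175, a difference of 0.175. Power with 110 per arm is then 0.844 (pooled) to 0.853 (Wald). The two rules do not estimate the same quantity.

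**4. MI.** No listed predictor records the Phase 2 findings or why a video is missing. Given those predictors, the model imputes as if a subject with a prevented view resembled those who were seen, so it does not correct this loss.

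**The case against.** Four arguments on the other side have force.

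- **Such subjects may not leave the analysis.** SAP 2.1 uses the non-missing denominator only by default, SAP 3.3.1 specifies all randomized, and Protocol 7.1.5 says that withdrawn subjects are included in the analysis. This stands as one of two conflicting readings. It does not settle the matter, because 8.7 and SAP 2.3.5 say otherwise and the interim CP uses evaluable subjects only.
- **A video largely covered by adhesions need not be invalid.** A reader might infer that hidden incisions are always discarded. The documents do not say so, and Grade 3 extent (over half the area) treats heavy coverage as gradable. The wording is unclear rather than exclusionary, and the firmer route is prevented laparoscopy. A clip that is merely too short is a recording failure, not loss caused by the outcome.
- **A reader might infer that the effect is biased towards the null.** That does not follow. The required field is wider in the treatment arm (application site plus surrounding areas), so loss could be greater there, which would enlarge the difference. Equal loss at the planning rates also enlarges it slightly.
- **A reader might infer that this loss explains the low rates that prompted the interim.** The documents attribute those to what investigators observed at the second procedure, not to centrally reviewed videos.

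**Conclusion.** The gap holds in a limited form. The plan has no outcome for adhesions at the target incision that block the required view or prevent laparoscopy. Its available-data rules and interim count lose such a subject, while its all-randomized denominator counts that subject as not free. The passages must be reconciled, and the planned MI analysis does not address the loss.

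The size is unknown. Over the assumed loss shares shown, a true difference of 0.15 is observed as anything from 0.094 to 0.168, and 5% loss in both arms barely moves it (0.146). The change from continue to stop at 94 subjects (CP 0.77 to 0.51) appears only under the assumed 30%/10% split and should not be read as a prediction. The point is a cheap improvement, not evidence that the result will be biased in a known direction.

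**What to change.** 1. In Protocol 7.1.2 and SAP 3.3.1, state that a Phase 2 video whose incomplete view is, in the blinded central reviewers' judgement, caused by adhesions at the target incision is scored adhesion present. Videos that are short or incomplete for any other reason stay non-evaluable, whether or not they show an adhesion. This limit matters: accepting deficient clips only when positive biases the rate upwards. With a true rate of 0.20 and 10% of videos deficient at random, the observed rate would be 0.20/(1 − 0.10·0.80) = 0.217.

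2. Pre-specify a sensitivity analysis, for both interim and final data, that also scores as adhesion present (i) an in-window reversal whose operative record says adhesions at the target incision prevented laparoscopic viewing and (ii) a death judged related to incisional adhesions.

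3. State one denominator for the primary proportion and align Protocol 8.1 and 8.7 with SAP 2.1, 2.3.5, 3.3.1 and 4. The sample size and the CP table are both built on evaluable subjects, so choosing all randomized would mean restating the power.

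The cost is protocol and SAP wording and an added line in the central reviewers' instructions, with no extra subjects or procedures. The sensitivity analysis relies on operative records and investigator judgement rather than on the blinded reviewers, so it should remain supportive.

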##### Secondary Endpoints

###### a. Extent of adhesions (including severity):

The extent of adhesions to the incision and abdominal wall between organs will be evaluated by the following grading scale respectively:

[figure not shown]
###### Severity

- Grade 1: filmy thickness, avascular
- Grade 2: moderate thickness, limited vascularity
- Grade 3: dense thickness, vascularized

###### Extent (percentage of the area covered by adhesion)

- Grade 1: mild, covering up to 25% of the total area and length
- Grade 2: moderate, covering 26%–50% of the total area and length
- Grade 3: severe, covering over 50% of the total area and length

For quantifying the extent of adhesions to the abdominal wall and between organs, the abdominal cavity will be divided into four abdominal quadrants as follows:

- b. **Incidence of patients with mechanical ileus:** defined as the mechanical ileus judged by investigators, which occurred 1 week after Phase 1 operation:
- c. **Incidence of patients with surgical site infections (SSI) following surgery:** according to the criteria of the US Centers for Disease Control (CDC) and Prevention of [22] as follows:

#### **CDC Definition of SSI**

##### **1. Superficial incisional SSI:**

Infection occurs within 30 days after the operation and infection involves only skin or subcutaneous tissue of the incision and at least one of the following:

- Purulent drainage, with or without laboratory confirmation, from the superficial incision;
- Organisms isolated from an aseptically obtained culture of fluid or tissue from the superficial incision;
- At least one of the following signs or symptoms of infection: pain or tenderness, localized swelling, redness, or heat and superficial incision, is deliberately opened by surgeon, unless incision is culture-negative;
- Diagnosis of superficial incisional SSI by the surgeon or attending physician.

##### **Do not report the following conditions as superficial SSI:**

- Stitch abscess (minimal inflammation and discharge confined to the points of suture penetration);
- Incisional SSI that extends into the fascial and muscle layers (see deep incisional SSI).

##### **2. Deep incisional SSI:**

Infection occurs within 30 days after the operation if no implant is left in place or within 1 year if implant is in place and the infection appears to, be related to the operation and infection involves deep soft tissues (e.g., fascial and muscle layers) of the incision and at least one of the following:

- Purulent drainage from the deep incision but not from the organ/space component of the surgical site;
- A deep incision spontaneously dehisces or is deliberately opened by a surgeon when the patient has at least one of the following signs or symptoms: fever ( $>38^{\circ}\text{C}$ ), localized pain, or tenderness, unless site is culture-negative;
- An abscess or other evidence of infection involving the deep incision is found on direct examination, during reoperation, or by histopathologic or radiologic examination;
- Diagnosis of a deep incisional SSI by a surgeon or attending physician.

Notes:

- Report infection that involves both superficial and deep incision sites as deep incisional SSI;
- Report an organ/space SSI that drains through the incision as a deep incisional SSI.

